2.2.1 Schedule of visits

Pre-treatment assessments will be performed during the 30 days prior to enrolment. After enrolment, study visits will be as follows:

- Study Day 0 will be the day the subject is enrolled.
- Study Day 1 will be the day of the PHO injection. Study Hour 0 will be the time of the end of PHO injection.
- Study Day 3 will be the day of PDT. Study Hour 40-50 will be calculated from Study Hour 0.
- Study Day 5 will be the day of hospital discharge. Subjects will be discharged from the 48-hour hospital stay after the Chest X-ray and other safety evaluations indicating that the subject is stable and able to be discharged; otherwise, the subject's hospital stay may be extended to 72 hours or until the subject is stable for discharge
- Study Day 13 to Day 18 will be the time-period where the surgery will be performed post PDT.
- Study Day 20 to Day 25 (±2 days) will be the 7-day post-surgery visit.
- Study Day 43 to Day 48 (± 3 days) will be the 30-day post-surgery visit.
- Study Day 103 to Day 108 (±7 days) will be the 90-day post-surgery last study visit.

3. DATA ANALYSIS CONSIDERATIONS

3.1 Determination of Sample Size

This study is designed to assess the safety of PDT in subjects with solid lung tumors prior to surgical resection and to assess the lung tumor and healthy tissue response to PDT. The intent of this study is to enroll 10 subjects. This sample size has the following precision for estimation of rates of AE's of special interest (AESI). The following table shows historical AE rates for RFA ranging from <1 to $\sim50\%$.

AESI	Rate Observed with RFA				
Pneumothorax	11-52%				
Pleural effusion	6-19%				
Hemorrhage	6-18%				
Pulmonary artery pseudoaneurysm	0.2%				
Needle tract seeding	0.3-0.7%				
Cavitation	14%				
Bronchopleural fistula	0.6%				
Pneumonitis	0.4%				

The sample size of N=10 has precision for estimation of AE rates for estimates ranging from <0.01 to ~0.5 as shown in the following list. Precision is measured by 1-sided 95% upper confidence limit (CL) on the estimated AE rate via exact binomial distribution. PDT is expected to have lower AE rates than RFA, so, for example, for a RFA historical rate of 0.27 (27%), if no such AE's are observed on PDT, then the TRUE underlying PDT rate is lower than 0.27 with 95% confidence since the upper 95% CL is 0.26 - indicated by "*" in the list below.

No. of AESIs	Rate	Upper 1-sided 95% confidence limit
0	0.00	0.26*
1	0.10	0.39
2	0.20	0.51
3	0.30	0.61
4	0.40	0.70
5	0.50	0.78

The study will be suspended and re-evaluated from a safety standpoint if 20% of the subjects experience a serious adverse event that is related to PDT.

4. PRIMARY AND SECONDARY ENDPOINTS

4.1 Primary Endpoints

The primary endpoints are safety assessments:

- incidence of adverse events and serious adverse events
- laboratory data
- physical examination
- vital signs
- concomitant medication

4.2 Secondary Endpoints

Secondary endpoints will include:

- Tumor destruction and cell death in area of the PDT (0.75 cm radius if the laser fiber is eccentrically placed, or 1.5 cm diameter if the laser fiber is centrally placed) as defined by cytological and pathological evaluation.
- Effect of PDT on the non-cancerous lung tissue surrounding the targeted tumor.

5. STATISTICAL METHODOLOGY

5.1 General Considerations

All statistical evaluations will be conducted using SAS® version 9.4 or higher (SAS® Institute, Cary, North Carolina). All tables, figures and listings will be produced in landscape format.

In general, all data will be listed by subject and visit/time point where appropriate. The total number of subjects under the stated population (N) will be displayed in the header of summary tables.

Data will be summarized using descriptive statistics for continuous variables. Unless otherwise specified, descriptive statistics will include number of subjects, mean, standard deviation, minimum, median and maximum. In case of n<2, where n indicates the number of evaluable subjects at the particular time point, the standard deviation will be empty. The statistic "Missing" will also be presented as the number of missing entries/subjects, if any at that visit/timepoint, and presented as a summary statistic only when non-zero. The minimum and maximum statistics will be presented to the same number of decimal places as the original data. The mean and median will be presented to one more decimal place than the original data, whereas the standard deviation will be presented to two more decimal places than the original data.

In summary tables of categorical variables, counts and percentages will be used. The count [n] indicates the actual number of subjects with a particular value of a variable or event, which should always be less than or equal to the total number of subjects with non-missing value of the variable or event [M]. Percentage will be obtained by: % = (n/M)*100. Unless otherwise stated, all percentages will be expressed to one decimal place.

In by-visit summary tables only scheduled visits/timepoints will be summarized. In listings all visits and timepoints with any data collected, including both scheduled and unscheduled ones and early termination visits, will be included.

The closest non-missing measurement (whether from scheduled or unscheduled visit) taken prior to the administration of the study drug (PHO) will be considered as the baseline value. The change from baseline values will be derived for each subject as the post-baseline evaluation minus the baseline evaluation.

Study days will be calculated as the number of days from the date of the study drug administration:

Study Day = (Target Date - Date of the study drug administration) + 1 if target date is greater than or equal to the date of the study drug administration or

Study Day = (Target Date – Date of the study drug administration) if target date is less than date of the study drug administration.

All dates will be displayed in DD/MMM/YYYY format.

5.2 Analysis Populations

The analysis populations defined in this study are as follows:

5.2.1 Intent-to-Treat Population

The Intent-to-Treat (ITT) Population will be defined as all enrolled subjects.

5.2.2 Safety Population

The Safety Population will be defined as all enrolled subjects who received the Photofrin® injection.

5.3 Coding Dictionaries Used

Adverse event and medical history verbatim terms provided by the investigator will be coded using the Medical Dictionary for Drug Regulatory Affairs (MedDRA, version 20.0). The resultant primary system organ class and preferred term will be used for AE summaries.

Prior and concomitant medication generic terms provided by the investigator will be coded according to WHO Drug Dictionary September-2016 B2 and classified by preferred terms and ATC classes. The highest available ATC class and preferred term will be used for prior and concomitant medication summaries and listings.

5.4 Analysis Methods

5.4.1 Study Subjects Disposition

Subject disposition will be summarized by presenting the number of subjects who were enrolled, were included into the ITT and safety populations, received PDT, underwent planned surgery, completed the study and prematurely discontinued with breakdown by the reason for early discontinuation. The analysis will be based on all enrolled subjects.

A listing will be presented to describe whether the subject completed the study, date of completion or early withdrawal, and the reason for early discontinuation, if applicable. A listing will also be provided to describe if the subject meets all inclusion/exclusion criteria. The reason for entry criteria violation, if any, will be presented.

5.4.2 Demographic and Baseline Characteristics

Demographic and baseline characteristics such as age, sex, childbearing potential (for female subjects only), race, ethnicity, height (cm), weight (kg) and BMI (kg/m²) as well as baseline ECOG status and skin phototype will be summarized. The analysis will be based on the Safety population and ITT population.

Descriptive statistics will be presented for age, height, weight, BMI. Frequency counts and percentage will be presented for sex, childbearing potential, race, ethnicity, ECOG status and skin phototype.

The demographic and baseline characteristic data will also be presented as a data listing.

5.4.3 Medical History

Medical history will be summarized by MedDRA system organ class and preferred term for the safety population.

Medical history details as collected on the CRF such as condition, MedDRA system organ class and preferred term, the date of onset, stop date and intensity of the condition will be presented in a by-subject data listing.

5.4.4 Primary Diagnosis and Oncology History

Primary diagnosis and oncology history findings collected at the CRF, such as whether the subject has primary or metastatic tumor, tumor size and whether it is completely resectable, location of primary tumor (for subjects with metastatic tumor), biopsy of cytology results will be summarized descriptively and listed.

5.4.5 Protocol Deviations

The study site will record all deviations occurred through the study on the CRF.

Protocol deviation frequencies will be summarized descriptively by deviation type.

All protocol deviations data collected on CRF will be presented as a by-subject data listing.

5.4.6 Photofrin® Injection

All details of Photofrin® injections collected on CRF will be listed.

5.4.7 Photodynamic therapy

All details of light application collected on CRF will be listed.

5.4.8 Surgery

All details of the planned surgery collected on CRF will be summarized descriptively and listed.

5.4.9 Tumor and Healthy Tissue Response Analysis

Macroscopic and microscopic examinations of the tumor and surrounding healthy lung tissue will be evaluated following the surgery. Findings collected on CRF will be summarized descriptively and listed.

5.4.10 ECOG Performance Status

ECOG performance status will be assessed at Screening, prior to PDT procedure, prior to surgery, at the Day 20-25, Day 43-48 and Study Exit visits. Number and percentage of subjects with each status will be presented by visit. All results will be listed.

5.4.11 Safety Analysis

All safety data will be listed and tabulated. The analysis will be performed on the Safety population.

Safety parameters include adverse events, laboratory data, physical examination findings, vital signs and concomitant medications.

5.4.11.1 Adverse Events

Adverse Events will be coded using the Medical Dictionary of Regulatory Activities (MedDRA version 20.0) AE coding system for purpose of summarization.

Events collected at the "NCS Events" CRF page will be summarized together with Adverse Events, but excluded from analyses by CTCAE grade and relationship to study drug, since these data points are not captured for NCS events.

An AE will be defined as treatment-emergent (TEAE) if its date of onset is on or after the date of the study drug (PHO) administration.

An AE will be defined as treatment-related if its relationship to the study drug is recorded as "Reasonable Possibility" on the CRF.

An overall summary of number and percentage of subjects with at least one AE, TEAE, serious TEAE, treatment-related TEAE, serious treatment-related TEAE, TEAE leading to discontinuation and fatal TEAE will be presented.

A summary of the frequency (number and percentage of subjects) of TEAEs will be presented by system organ class and preferred term. One-sided 95% upper confidence limit will be computed for each AE percentage via exact (Clopper-Pearson) method for binomial proportion. Adverse events will also be analyzed by their CTCAE grade (1 to 5) and relationship to study drug (related or not related).

A subject experiencing the same AE multiple times will be counted only once for that preferred term. Similarly, if a subject experiences multiple AEs (preferred terms) within the same system organ class, then that subject will be counted only once for that system organ class. When summarizing by CTCAE grade and relationship, only event with highest grade or relationship will be counted. All AEs will be presented in alphabetical order of SOC and preferred terms.

Skin photosensitivity is an adverse event of special interest (AESI). Skin photosensitivity will be summarized separately by SOC and preferred term as well as by SOC, preferred term and CTCAE grade.

All information pertaining to adverse events noted during the study will be listed by subject, detailing verbatim term given by the investigator, preferred term, system organ class, start date, stop date, CTCAE grade, outcome, action taken and drug relatedness. Separate listings will be created for Serious TEAEs, TEAEs leading to study drug discontinuation and skin photosensitivity events.

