## 8. ASSESSMENT OF SAFETY

Any adverse event/concurrent illness experienced by a subject during any portion of the study must be described in detail and be fully evaluated by the investigator. The investigator is responsible for recording and reporting all adverse events observed or reported during the study from informed consent signature until date of completion/discontinuation, regardless of drug-related assessment and/or clinical significance. Any pertinent information must be recorded in the Case Report Form (CRF) and additional comments describing the course and outcome of these events should be provided as appropriate.

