##### 10.5.3. Safety Analysis

Safety analysis will be performed on the Safety Population.

The number and percentage of subjects with normal and abnormal findings will be provided for each physical examination in a shift table comparing screening and the end of study evaluation.

Vital signs will be summarized descriptively (mean, standard deviation, median, minimum and maximum). Change from baseline will also be summarized.

Skin photosensitivity is an adverse event of special interest and will be summarized separately from other adverse events at each safety assessment. Changes in skin will be assessed by grade of erythema, edema and blistering. The data will be tabulated by CTCAE grade in the Dermatology/Skin category.

Descriptive statistics for each clinical laboratory test will be presented for the baseline and the end of study assessment. Change from baseline will also be summarized. According to the laboratory normal ranges, laboratory test results will be categorized as low (< lower limit of normal, LLN), normal (within normal range), and high (> ULN). Shift tables, comparing the distributions of these three categories at baseline versus the end of study assessment, will be presented.

---

Concomitant medications will be coded using the WHO Drug dictionary. Medications initiated prior to start of treatment and maintained during the study, or taken during the course of the study will be considered as concomitant medications. Concomitant medications will be summarized according to the preferred terms only.

Adverse events will be coded using the Medical Dictionary for Regulatory Activities (MedDRA). The number and percentage of subjects who experienced any AEs as well as serious AEs will be presented by system organ class (SOC) and by preferred term (PT) within SOC. All AEs will be similarly presented by intensity (mild, moderate, severe or using the CTCAE grading system) and by relationship to treatment (reasonable possibility/no reasonable possibility). One-sided 95% confidence limit will be computed for each AE percentage via exact binomial method (Clopper-Pearson, 1934).

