6. CHANGES IN ANALYSIS FROM PROTOCOL

There are no changes from the protocol-specified analyses.

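### NCS events count towards AE incidence but drop out of the grade and relationship tables, so related incidence may be understated, and SAP section 6 declares no departure

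*SAP*

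**What the plan says.** The primary endpoints in SAP section 4.1 begin with "incidence of adverse events and serious adverse events". Section 5.4.11.1 pools events from an NCS Events CRF page with adverse events in the summaries, "but excluded from analyses by CTCAE grade and relationship to study drug, since these data points are not captured for NCS events". The same section calls an AE treatment-related only if the CRF records a reasonable possibility of relationship, and tabulates relationship in two levels, related and not related. It plans no not-assessed row and no separate NCS count. It also tabulates skin photosensitivity twice, once by preferred term and once with CTCAE grade added.

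The protocol mentions no NCS page or category in its text. Section 8 requires investigators to record all adverse events "regardless of drug-related assessment and/or clinical significance". Sections 8.4.1, 8.4.2 and 8.4.3.2 have each AE entered on the Adverse Event Form, graded for intensity and assessed for causality. For the analysis, section 10.5.3 says: "All AEs will be similarly presented by intensity (mild, moderate, severe or using the CTCAE grading system) and by relationship to treatment".

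SAP section 6 states: "There are no changes from the protocol-specified analyses".

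**The concern.** An event with no causality judgment raises all-cause incidence and cannot raise related incidence. In the overall summary, where the two rows stand together, it therefore reads as an unrelated event, although nobody judged it so. The same event counts in the system organ class and preferred term table and is absent from the grade table.

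AE incidence is the primary endpoint, and the study plans only 10 subjects, so a single subject is visible in every rate. A reader who compares the incidence, grade and relationship tables could find that they differ, with nothing in the tables to explain why. A reader who relies on section 6 would not know that the AE analysis differs from the protocol's.

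**Working it through.** **Inputs**

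- Sample size, SAP section 3.1: "The intent of this study is to enroll 10 subjects". I assume all 10 receive the injection, so the Safety Population is also 10.
- Interval, SAP section 3.1: "Precision is measured by 1-sided 95% upper confidence limit (CL) on the estimated AE rate via exact binomial distribution". SAP section 5.4.11.1 applies it: "One-sided 95% upper confidence limit will be computed for each AE percentage via exact (Clopper-Pearson) method for binomial proportion".
- Percentages, SAP section 5.1: n/M, where M counts subjects with a non-missing value.
- Number of NCS events, and how many would have been judged related: not given. Steps 3 and 4 therefore use assumed values over a range.

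**Step 1. Reproduce the plan's own limits.** The upper limit U for x subjects out of 10 solves P(X ≤ x | 10, U) = 0.05. For x = 0 this is U = 1 − 0.05^(1/10) = 0.2589.

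| x | U | SAP section 3.1 |
|---|---|---|
| 0 | 0.2589 | 0.26 |
| 1 | 0.3942 | 0.39 |
| 2 | 0.5069 | 0.51 |
| 3 | 0.6066 | 0.61 |
| 4 | 0.6965 | 0.70 |
| 5 | 0.7776 | 0.78 |

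All six agree to two decimals.

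**Step 2. One term, one subject whose only event under it is an NCS event, no other subject affected.**

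- Incidence table: 1/10 = 10%, upper limit 0.39. Without NCS events it would be 0/10, limit 0.26.
- Sum of the grade rows: 0. Sum of the relationship rows: 0.
- Gap: 1 subject, or 10 percentage points.

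The worked example in SAP section 3.1 sets the zero-event limit of 0.26 below a historical RFA rate of 0.27. With this one event the limit is 0.39, and that comparison no longer succeeds for the term.

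If the subject also has a graded and assessed AE under the same term, the tables still agree.

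**Step 3. Related count.** Assume 2 subjects have a TEAE recorded as related. Assume k further subjects have an NCS event that would have been judged related, and no other related TEAE.

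| k | reported | had causality been assessed | upper limit at that count |
|---|---|---|---|
| 0 | 2/10 | 2/10 = 20% | 0.51 |
| 1 | 2/10 | 3/10 = 30% | 0.61 |
| 2 | 2/10 | 4/10 = 40% | 0.70 |
| 3 | 2/10 | 5/10 = 50% | 0.78 |

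The count is never too high. It is too low by k, and k may be 0. The limits are for scale only: the SAP places its sentence on limits with the preferred-term summary and does not clearly extend it to the relationship rows.

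**Step 4. Related percentage.** If subjects with no relationship recorded leave M, the same 2 related subjects give 2/10 = 20.0%, 2/9 = 22.2%, 2/8 = 25.0% or 2/7 = 28.6% for 0, 1, 2 or 3 such subjects. The SAP does not say whether they leave M, so the reported percentage could rise while the count stays the same or is too low.

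**Step 5. The two possible readings of an NCS event.**

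- It is a protocol AE. Protocol section 8 makes clinical significance irrelevant to recording, so it belongs in incidence. Leaving it out of the grade and relationship analyses then departs from protocol section 10.5.3.
- It is not a protocol AE. Section 10.5.3 does not reach it, but counting it in AE incidence changes the primary endpoint and can raise its rates and limits.

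On both readings the SAP analysis differs from the protocol's.

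**The case against.** The strongest reply has four parts.

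- **The SAP is open about the rule.** It gives the exclusion and the reason for it, and events cannot be tabulated by an item that was not collected. By-subject listings let a reader trace individual events among 10 subjects, and the study is descriptive. This stands, and it limits the harm. It does not supply a reconciling row, a denominator or an accurate section 6.
- **NCS events may not be AEs.** Protocol section 8.3 makes a laboratory abnormality an AE only above a severity threshold or when it is clinically significant, so some non-AE findings on that page are plausible. Related-AE incidence would not then be understated. This also stands, but it moves the problem to the primary incidence rather than removing it.
- **Part of the record was not available to me.** Protocol section 8.1 refers to a flow chart on how to document an AE. The text I worked from does not show it, nor the CRF or most of the SAP abbreviation list. The chart may define a separate route for these events, and no criticism is made of the missing expansion of NCS. Even if the chart settles their status, one of the two readings in Step 5 still applies.
- **Counting NCS events in incidence is the cautious choice.** This stands. A reader might infer that they should be moved out of the primary table. If they are protocol AEs, that would remove required events and lower the reported incidence, so the documents do not support it.

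**Conclusion.** The point holds in conditional form. Treatment-related incidence may be understated, and its denominator is unclear. The grade and relationship tables will not reconcile with the incidence table for any term where a subject's only event is an NCS event. With 10 subjects in the Safety Population, each affected subject is worth 10 percentage points, and the first moves a term's upper limit from 0.26 to 0.39.

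A reader might go further and conclude that related incidence is understated, or that the tables cannot reconcile. The documents do not support either. They give no NCS count and no sign that any NCS event would have been judged related. Understatement needs at least one such event in a subject with no other related TEAE, overall or for the term in question. The mismatch needs a subject with no other event under the term. If neither occurs, the figures are unaffected.

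The part that does not depend on counts is the statement in SAP section 6. It should be corrected whichever way the status of NCS events is settled.

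**What to change.** In SAP section 5.4.11.1:

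1. State whether NCS events meet the protocol's AE definition.
2. Keep them in the primary incidence table, and also show incidence and exact limits without them.
3. Add a not-assessed row to the grade and relationship tables, including the skin photosensitivity grade table. It should hold subjects whose only event for the term is an NCS event, so that the rows sum to the incidence table.
4. State that percentages in these tables use the Safety Population as denominator, so that unassessed subjects do not leave M.
5. Add a supportive treatment-related count that treats unassessed causality as related. It should include every subject with a treatment-emergent NCS event, including those who also have an AE judged unrelated.

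In SAP section 6, list the handling of NCS events as a departure from protocol section 10.5.3 or, if they are not AEs, as an addition to the primary AE incidence.

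The cost is SAP wording, one or two extra tables and a slightly less favourable bounding figure for related events. No new data are needed. The change does not recover the missing grades and causality judgments; it shows how much depends on them.

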### 5.2. Treatment Procedures

Treatment procedures will consist of three periods: Period I – PDT Course; Period II – Surgery; and Period III – Follow-up.

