#### *5.2.1.3. Study Day 5 (Hospital Discharge Evaluation)*

Approximately 48 hours after PDT bronchoscopy, the following safety evaluations will be performed to determine if subjects are medically stable to be discharged from the hospital.

1. Vital signs (pulse, blood pressure, temperature, and respiration rate).

2. Clinical labs (Appendix 13-4).
3. Chest X-ray.
4. Record concomitant medications and adverse events.

*5.2.1.3.1. Subject medically stable*

Discharge subject and provide instructions on how to manage light exposure.

*5.2.1.3.2. Subject non-medically stable (Day 6 to Day 10 -Extended hospitalization as required)*

The subject's 48-hour hospitalization can be extended to 72 hours (or longer) at the discretion of the investigator if the subject is deemed medically unstable. During this extended hospitalization, the following assessments should be performed daily until the subject is considered stable and able to be discharged.

1. Vital signs (pulse, blood pressure, temperature, and respiration rate).
2. Record concomitant medications and adverse events.

The day of the discharge, the following assessments should be performed.

1. Clinical labs (Appendix 13-4).
2. Chest X-ray.

The prolongation of hospitalization after 72 hours due to subject being medically unstable is to be reported to the sponsor as a serious adverse event. If a subject is still hospitalized at Day 10, the sponsor should be notified promptly.

*5.2.2. Period II - Surgery (Study Day 13 to Day 18)*

All subjects will undergo surgery as per standard of care 10 to 15 days after PDT. The following assessments will be performed.

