#### NO REASONABLE POSSIBILITY

- The AE is definitely not associated with PDT-Photofrin®;
- The AE does not follow a reasonable temporal sequence from PDT-Photofrin® administration;
- The AE does not disappear or decrease on discontinuation of PDT-Photofrin® (dechallenge) and/or does not reappear or increase on repeated exposure (rechallenge);
- The AE is reasonably explained by known characteristics of the subject's clinical state, history, environment, other therapy administered to the subject (drug or non-drug); and/or
- The AE may be caused by reasons other than administration of PDT-Photofrin®.

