2.2 Study Design

This is a prospective, multicenter, uncontrolled, non-randomized, open-label, clinical study with the primary objective to assess safety of PDT in subjects with peripherally located malignant tumors in lung parenchyma prior to surgical resection. A Time and Procedures Schedule for the overall conduct of the study is outlined in section 8.

The primary diagnosis will be performed as per standard of care no more than 60 days prior to consent signature. Upon signing consent, subjects will be assigned a unique participation number and will undergo screening evaluation conducted during the 30 days prior to enrollment. This phase will involve medical evaluations and thorough review of all reports that led to the primary diagnosis. Upon successful screening evaluations, subjects will be enrolled into the study.

Treatment Procedures will consist of one PDT-Photofrin® course performed through navigational bronchoscopy or peripheral ultrasound guided bronchoscopy. One course will consist of an intravenous (IV) injection of Photofrin® (PHO) 2 mg/kg over 3-5 minutes followed by one laser light application session. The end of injection will be Study Hour 0. Photodynamic laser therapy will be performed on Study Hour 40-50. Laser light (630 nm wavelength) will be applied at a dose of 200 J/cm of the diffuser length.

Ten to 15 days after PDT, subjects will undergo surgery as per standard of care. Macroscopic and microscopic examinations of the tumor and surrounding healthy lung tissue will be evaluated to determine the effect of PDT on the tumor and the healthy/non-tumor lung tissue. Macroscopic examinations will be performed at the local institution. Microscopic examinations will be performed by a central reader pathologist.

Follow-up assessments will include some or all the following procedures: physical exam; vital signs evaluation; body weight measurement; chest CT; chest X-ray; performance status; and clinical laboratory testing. All subjects will be asked general questions about the occurrence of adverse events, concurrent medical conditions, use of adjunctive therapy/procedure, and intake of concomitant medication.

Data will be analyzed to evaluate the safety of the modality up to 90 days post-surgery.

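### The all-causality adverse event rates and upper limits combine PDT with the lung resection planned for every subject, and no adverse event table splits onset at surgery

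*SAP*

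**What the plan says.** SAP 5.4.11.1 defines the counted events by their start only: "An AE will be defined as treatment-emergent (TEAE) if its date of onset is on or after the date of the study drug (PHO" administration date. It sets no end. Protocol section 8 has adverse events recorded until completion or discontinuation, and SAP 2.2 gives the horizon: "Data will be analyzed to evaluate the safety of the modality up to 90 days post-surgery". Protocol 5.2.2 states: "All subjects will undergo surgery as per standard of care 10 to 15 days after PDT". SAP 2.2.1 puts surgery on Day 13-18 and the last visit on Day 103-108 (±7 days).

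The outputs in SAP 5.4.11.1 are an overall summary, TEAEs by system organ class and preferred term with exact one-sided 95% upper limits, breakdowns by CTCAE grade and by relationship, and a separate photosensitivity summary. A subject counts once per preferred term over the whole window. Protocol 10.5.3 asks for the same kind of limit: "One-sided 95% confidence limit will be computed for each AE percentage via exact binomial method".

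The structure needed for a split already exists. Protocol 5.2 says "Treatment procedures will consist of three periods", namely PDT course, surgery and follow-up, and the SAP schedule table repeats them. No adverse event table uses them.

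**The concern.** The primary objective is the safety of PDT before resection. SAP 3.1 justifies ten subjects by the upper limits and reads them against historical radiofrequency ablation rates for terms such as pneumothorax, pleural effusion and hemorrhage. The SAP counts such a term under the same heading whether it arises after light delivery or after the operation. A reader of the all-causality table cannot tell how much of a rate arose before resection. If the same subject has the same term both before and after surgery, the count-once rule merges the two. What is at stake is the interpretation of the main safety table. No test or decision rule turns on it.

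**Working it through.** **Inputs.** N = 10 and the limits for 0 to 5 events (SAP 3.1). Injection Day 1, light Day 3, surgery Day 13-18, exit Day 103-108 ±7 (SAP 2.2.1). Exact one-sided 95% Clopper-Pearson limit (SAP 5.4.11.1).

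**Step 1: the plan's own figures.** With x subjects affected out of n, the upper limit is the 0.95 quantile of a Beta(x+1, n−x) distribution. For n = 10 and x = 0 to 5 this gives 0.259, 0.394, 0.507, 0.607, 0.697 and 0.778. These round to the SAP's 0.26, 0.39, 0.51, 0.61, 0.70 and 0.78, so the table is correct.

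**Step 2: share of the window, in days, Day 1 to exit inclusive.**

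| Surgery / exit | Injection to before light | Light to before surgery | Surgery to exit |
|---|---|---|---|
| Day 13 / Day 103 | 2 | 13 − 3 = 10 (10%) | 103 − 13 + 1 = 91; 91/103 = 88% |
| Day 18 / Day 108 | 2 | 18 − 3 = 15 (14%) | 108 − 18 + 1 = 91; 91/108 = 84% |

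With the ±7-day exit window the last share is 84/96 = 87.5% to 98/110 = 89.1% for Day 13 surgery, and 84/101 = 83.2% to 98/115 = 85.2% for Day 18. Overall that is 83-89%.

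**Step 3: effect on a limit, all 10 subjects receiving light.** Suppose a term has no case between light and surgery and one case after surgery. The light-to-surgery limit is 0.26 (0/10) and the pooled limit is 0.39 (1/10). The SAP's example, in which no events puts the PDT rate below 0.27, would then not be available from the pooled table.

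In reverse, a pooled count of X is compatible with 0 to X cases between light and surgery:

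| Pooled count | Pooled limit | Compatible light-to-surgery limit (n = 10) |
|---|---|---|
| 1 | 0.39 | 0.26-0.39 |
| 2 | 0.51 | 0.26-0.51 |
| 3 | 0.61 | 0.26-0.61 |

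**Step 4: fewer subjects receiving light.** The Safety Population is defined by the injection, so the denominator for the light-to-surgery period can be smaller. For zero or one case, n = 9 gives 0.28 or 0.43 and n = 8 gives 0.31 or 0.47. A pooled count of 1 is then compatible with 0.28-0.43 or 0.31-0.47, and the top of each range exceeds the pooled 0.39.

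**Step 5: direction.** At fixed n the limit rises with x, and the pooled count is never below the light-to-surgery count. On the same denominator, pooling can therefore only raise the limit.

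**The case against.** **The listings already show the timing.** SAP 5.4.11.1 lists every adverse event by subject with its start date, and SAP 5.4.7 and 5.4.8 list light application and surgery. With about ten subjects, a reader can place each event by hand. This stands and lowers the importance of the point. A reader might infer that the planned report hides when events occurred; it does not. What the listings lack is period rates, denominators, limits, and a prespecified rule for same-day events.

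**Relationship is already tabulated.** Protocol 8.4.2 allows an event to be called unrelated when it is explained by "other therapy administered to the subject (drug or non-drug"), which could cover surgery. In the relationship summary "only event with highest grade or relationship will be counted", so a related case before surgery is not lost there. This stands in part. The separation rests on unblinded judgement in a single-arm study, and events from the NCS page carry no relationship. Onset date is an objective complement.

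**The pooled window is a stated choice.** SAP 2.2 says openly that safety runs to 90 days after surgery, and Protocol 7.1 notes that photosensitivity can last 90 days or more. This stands: the pooled limits are still needed.

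**A split by date can undercount PDT events.** The only scheduled CT between PDT and resection belongs to the surgery visit (Protocol 5.2.2, assessments prior to surgery) and may fall on the operation date. Sending every surgery-date onset to the surgical period would move a PDT effect first seen on that CT into the wrong period, in the favourable direction. This is right, and the fix has to deal with it.

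**Conclusion.** The point holds as a gap in presentation, at the lowest severity. The all-causality rates and limits describe PDT plus resection, and no planned table gives rates or limits by onset relative to surgery.

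Three stronger readings are tempting, and the documents do not support them:

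- That pooling makes PDT look safer. On the same denominator it can only raise the limits.
- That it undermines the safety stop. The suspension rule in SAP 3.1 counts serious events related to PDT, so all-causality pooling leaves it largely unaffected.
- That 84-88% of events will be surgical. That figure is a share of planned calendar days. The documents give no post-resection event rate, so no count can be predicted.

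The step from 0.26 to 0.39 is an illustration. It assumes that all 10 subjects receive light and that one subject has the term only after surgery. The analysis is descriptive and no formal test changes.

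**What to change.** In SAP 5.4.11.1, add TEAE and serious TEAE tables by onset period:

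1. Injection to before light.
2. Light to before surgery.
3. Surgery to study exit.

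Count each subject once per preferred term within each period, and include the terms listed in SAP 3.1. For period 2, give exact one-sided 95% upper limits among subjects who received light. Show them beside the pooled Safety Population limits, which stay.

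Prespecify these rules:

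- Onset on the surgery date goes to period 3, except that findings first recorded on the pre-surgery CT or another pre-surgery assessment count in period 2.
- Footnote all same-day events, and show the period 2 limits with ambiguous surgery-date events counted both ways.
- State when period 2 ends for a subject who received light but had no surgery.
- Keep photosensitivity on the full window.

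The cost is SAP wording and a few tables. Onset dates, light details and surgery details are already collected, and SAP 5.4.1 already counts subjects who received PDT and who underwent surgery. The downside is more sparse tables. PDT effects that first appear after surgery must still be read from the pooled table.
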